## **STUDY SITE**

Proposed Study Site: Patan Academy of Health Sciences, Patan Hospital, Lalitpur

#### 1. ABSTRACT

In the absence of a microbiological lab testing, majority of the cases of febrile illnesses in Nepal are diagnosed on a clinical basis alone. These cases of "undifferentiated febrile illness" are treated empirically with multiple antibiotics without an etiological diagnosis. Unnecessary use of antibiotics can increase the risk of antibiotic resistance and adds unnecessary burden of cost to the patients and their families.

This study aims to determine the etiology of infections using additional microbiological techniques in patients admitted to the hospital with acute undifferentiated febrile illness of 3 days to 21 days duration, and assess its impact on use of antimicrobial drugs. In addition to the clinical features, the etiological diagnosis will be confirmed by using additional tests including culture techniques and ELISA based serological tests for 7 additional pathogens which are currently not tested in Nepal. Patients meeting definition of undifferentiated fever of 3 days to 21 days duration will be enrolled from a major tertiary care center using predefined inclusion and exclusion criteria.

This study will help to identify additional infectious diseases prevalent in Nepal, decrease unnecessary empirical use of multiple antibiotics, and improve patient outcome. Additionally, identification of new causes of febrile illness will help in prevention and control of these infectious diseases at public health level.

#### 2. BACKGROUND AND RESEARCH GAP

Nepal is located between latitudes 26° and 31°N while its altitude ranges from 60m to 8848m from sea level allowing for a large variation in climate. Southern part of Nepal has tropical climate suitable for vector-borne tropical diseases whereas northern parts have more temperate and sub-arctic climate where these diseases are less common. Additionally, water-borne diseases have persisted because of a

lack of sanitation and safe drinking water. Most hospitals in Nepal lack support of well equipped microbiology laboratories for diagnosis of infectious diseases, and hence, most clinicians treat their patients empirically based on their decisions on clinical features alone [1,2]. A study done in the region has shown poor predictability of clinical features alone to distinguish enteric fever from other causes of febrile illness [3].

Either from the lack of or limited access to confirmatory microbiological tests, majority of the cases of febrile illnesses in Nepal are diagnosed on clinical basis only. These cases of "undifferentiated fever" or "undifferentiated febrile illness" are treated empirically without etiological diagnosis. In the absence of correct diagnosis, patients receive multiple empirical antibiotics which increase the risk of antibiotic resistance and adds unnecessary burden of cost to the patients and their families. A hospital-based study of febrile patients published in 2004 revealed identifiable causes in only 37% of the patients [4]. The most common causes of febrile illness in Nepal at the time were enteric fever, murine typhus, scrub typhus, Leptospirosis, and bacterial infections including *Streptococcus pneumoniae*, *Staphylococcus aureus*, and *Escherichia coli*. Studies show a trend in increasing cases of rickettsial infections including *Rickettsia typhi* and *Orientia tsutsugamushi* [4-6].

## Preliminary work done at Patan Hospital

Patan Hospital is a tertiary care medical center with 450 beds that admits between 10 to 30 febrile patients per week depending on the season. Over 30% of these patients do not have localizing signs and symptoms for clinical diagnosis nor do they have a laboratory-based diagnosis. These cases are labelled as undifferentiated fever and receive empirical treatment with two or more antimicrobial agents. Previous studies done at Patan Hospital have demonstrated that *Salmonella typhi* and *Salmonella paratyphi A* were causes of undifferentiated fever of >3 days duration in 34% patients and *Rickettsia typhi* in 17% cases, whereas another study in 2008 found 7% cases of febrile illness has *Rickettsia typhi*, which is the cause of Murine typhus [5,6]. These studies show an increase in cases of rickettsial infections including *Riackettsia typhi* and *Orientia tsutsugamushi*. Studies at Patan Hospital have also identified *Streptococcus pneumoniae*, *Leptospira* spp., *Orientia tsutsugamushi*, Hantavirus, and *Coxiella burnetii* as casues of febrile illnesses [4-6].

#### Research Gap

The epidemiology of infectious disease has changed with massive within country urban migrations, increased migrant workers to India and overseas countries, change in climate, and several other reasons. Previous common causes of febrile illnesses such as malaria and enteric fever have declined over past decade whereas dengue and scrub typhus are on the rise [7-9]. Meanwhile, new diseases such as COVID-19, dengue, and Scrub typhus have become commonplace [5,10,11]. Other causes of febrile illnesses, such as zoonoses (e.g. bartonellosis and Q fever), rickettsial (e.g. Q fever), and viral infections (e.g. arboviruses) remain mostly undiagnosed. This study aims to fill the gap in research by identifying additional causes and estimating burden of these infectious diseases. This will also help to reduce the unnecessary use of antibiotics.

#### 3. SIGNIFICANCE AND INNOVATION

#### A. Significance

This study is expected to identify additional infectious diseases prevalent in Nepal with the laboratory confirmation of the etiologic agents and improve the appropriate use of antimicrobial agents with targeted therapy. The laboratory tests used in this study will help to determine the presence of additional infectious diseases whose prevalence is currently unknown. This information will be helpful to the clinicians to design initial empiric antibiotic therapy based on epidemiological and clinical features. A more appropriate choice of antibiotics will decrease the unnecessary use of multiple broad-spectrum antibiotics, which in turn will help to reduce antimicrobial resistance, and improve patient outcome. New information discovered from the study will be useful for making policies to prevent and control various infectious diseases such as vector-borne infections and other communicable diseases.

## B. Innovation and discovery

The investigators aim to introduce and use selected lab technology with a higher sensitivity and specificity for laboratory confirmation of the diagnosis. We expect to identify new organisms causing febrile illness which are not detected with the currently used routine laboratory tests. Besides confirmation of the diagnosis, this study also plans to compare the clinical diagnosis alone as a guiding tool for the use of empirical antimicrobial therapy versus use of microbiological diagnosis. Hence, we will estimate the overuse and inappropriate use of antibiotics that may lead to antimicrobial resistance. The results and data from this study will be published and shared to educate the clinicians, reduce inappropriate antimicrobial therapy, and improve patient outcome.

#### 4. OBJECTIVES AND SPECIFIC AIMS

## A. Overall Objectives and Hypothesis

This study aims to determine the etiology of infections using laboratory methods in patients admitted to the hospitals with acute undifferentiated febrile illness and assess its impact on the use of antimicrobials. In addition to the clinical features of the patients, rapid serological tests and culture techniques will be used to confirm the etiological diagnoses.

We hypothesize that improved determination of etiological diagnoses in patients presenting with undifferentiated febrile illness can decrease the use of broad-spectrum antimicrobials.

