## **B.** Specific Aims

Primary:

- 1. To estimate the proportion of additional infectious etiologies of febrile illness among patients presenting with an undifferentiated fever of 3 to 21 days duration.
- 2. To compare the use of antimicrobials in patients with undifferentiated fever in whom additional microbiological tests have been performed versus patients with clinical diagnosis alone.

Secondary:

- 3. To evaluate the appropriateness of the empiric antibiotic therapy based on clinical diagnosis alone and after laboratory confirmation.
- 4. To estimate the correlation between clinical diagnosis with laboratory diagnosis in patients with undifferentiated fever.
- 5. To compare the outcome among patients whose treatment is based on microbiological diagnosis compared to the patients whose treatment is based on clinical diagnosis alone.

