## Additional Evaluations for the Study

For patients without an obvious cause of fever and an inconclusive work up after standard of care evaluations, additional serological tests as a part of undifferentiated febrile illness work up will be performed, including:

- a. Clinical evaluation: includes thorough history and physical examinations based on a standard questionnaire and data collection tool
- b. Additional Microbiological Evaluations: If above listed laboratory and microbiological tests do not indicate a conclusive diagnosis, the patient's blood will be processed for additional Serological tests as a part of undifferentiated febrile illness work up. These tests will help to establish diagnosis of the following infections:
  - Murine typhus
  - Bartonellosis
  - Q-fever
  - Chikungunya
  - 7ika
  - Japanese B encephalitis
  - West Nile virus
- 5. Use of antimicrobials in the patients with and without an etiological diagnosis and their outcome at the time of discharge from the hospital will be recorded.
- g. Laboratory Methods

For the purpose of the study, following samples will be collected from 50% of randomly assigned patients for additional microbiological testing.

- 1. Blood cultures, 2 sets from 2 different sites from all study patients (20 mL total)
- 2. Serum samples for serological testing (4 mL)

After obtaining appropriate consent, total 25 mL blood will be collected from each patient assigned to the additional testing arm. Blood samples will be cultured in liquid media and held in the incubator for 7-days.

Urine will be taken to the lab for routine examination and culture will be performed only if there are >10 pus cells or patient reports urinary symptoms.

Gram stain, AFB stain and Genexpert will be performed on sputum samples.

As a part of routine febrile illness work up, the serum samples will be tested for HIV, scrub typhus, dengue, leptospirosis, brucella, malaria, and kala azar.

Additional serum sample will be processed for further serological testing for Chikungunya, Zika, *Coxiella burnetii* (Q-fever), *Bartonella henselae* (Bartonellosis), *Rickettsia typhi* (murine typhus), Japanese B encephalitis, and West Nile virus using ELISA and/or Rapid Diagnostic Test (RDT), as applicable. Although molecular tests have a higher sensitivity and specificity, molecular testing has not been planned for this study because of the budget limits.

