## j. Data Collection, Data Analysis and Sample Size

Demographic, clinical, radiological, and laboratory data will be collected and entered into a password protected database. To minimize the errors, data will be directly entered into the database using REDCap Database questionnaires.

Data analysis will include the followings:

- 1. Demographics and baseline characteristics of patients will be analyzed and compared between the two groups.
- 2. Clinical diagnosis and laboratory confirmation of diagnosis will be used to estimate the proportions of various infectious etiologies of febrile illness in patients presenting with a febrile illness of 3-21 days duration. (Specific aim-1)
- 3. Number, type, dose and duration of antimicrobials used to treat the patients will be collected and compared between the two groups: clinical diagnosis alone versus clinical plus microbiological diagnosis. (Specific aim 2)
- 4. Appropriateness of the empiric antibiotic therapy will be determined by an independent physician expert after the laboratory confirmation of the diagnosis. Comparison between the two groups (clinical diagnosis vs. microbiological diagnosis) will be done by calculating the proportion of cases who received appropriate antibiotics divided by the total number of cases for whom empiric antibiotics were administered. (Specific aim-3)

- 5. Pretest probability for clinical diagnosis and posttest probability after laboratory-based diagnosis will be calculated and correlated for bacterial, rickettsial, viral infections versus other causes of fever. (Specific aim-4)
- 6. Clinical outcomes will be compared for patients whose treatment is based on clinical diagnosis alone (Group 1) versus the patients whose treatment is based on clinical plus microbiological diagnosis (Group 2). Composite Positive outcome (complete or partial recovery) and Negative outcome (in-hospital death) will be compared between the two groups. (Specific aim-5)

Demographics and baseline characteristics of patients will be expressed in percentages, means±SD, 95% confidence intervals, and/or median±IQR, as appropriate. Proportions will be compared between the two groups with Chi-square tests. Numerical variables will be expressed as Means/SD/95% confidence intervals and Median/IQRs, whereas Student T test or Mann-Whitney test, respectively, will be used for statistical comparisons. Alpha will be set at 95% (level of significance, p <0.05).

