For Specific aims 2 and 3, total daily defined dose (DDD) for each antimicrobial agent received by patients will be calculated following WHO guidelines. The total DDD, number of antibiotics, and Duration of antibiotics used will be compared between the groups by calculating Means/SD/95% confidence intervals. Similarly, appropriateness of antibiotic uses will be tested with cross-tabulation using Chi-square analysis.

For specific aim 4, pre-test probability and post-test probability will be determined by both using standard calculations and using Fagan's Nomogram. Correlations between pre- and post-test probabilities for bacterial, rickettsial, viral vs. other causes will be evaluated.

For specific aim 5, the hazard ratio using the Cox proportional hazard model will be calculated to compare the outcomes between the groups. Since multiple factors, such as comorbidities, severity of illness at baseline, type of infection and host immune status, can influence the outcomes, adjustment for these factors will be considered during the univariate and multivariate outcome analyses. Updated Charlson comorbidity index (Quant et al.) will be calculated and used for comparison between the groups [15]. Similarly, qSOFA will be used to stratify the patients by severity of infection [16].

REDCap (Research Electronic Data Capture) software will be used for questionnaire and database entry. SPSS version 25 (IBM, USA) will be used for statistical analysis.

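### The hypothesis concerns broad-spectrum antimicrobials, but the aim 2 measures and the sample size count all agents regardless of spectrum, so a switch to targeted treatment can be diluted, hidden or reversed

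*Protocol*

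**What the plan says.** Section 4.A states a single hypothesis: improved diagnosis in patients with "undifferentiated febrile illness can decrease the use of broad-spectrum antimicrobials". Section 3.A gives the reasoning, which is that laboratory confirmation allows targeted therapy and so less use of several broad-spectrum drugs.

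Primary aim 2 (section 4.B) is wider: "To compare the use of antimicrobials in patients with undifferentiated fever in whom additional microbiological tests have been performed", against patients with a clinical diagnosis alone. For its analysis, section 5.j says first: "Number, type, dose and duration of antimicrobials used to treat the patients will be collected and compared between the two groups". It then names the measures: "The total DDD, number of antibiotics, and Duration of antibiotics used will be compared between the groups".

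The sample size section assumes a decrease in antibiotics from 90% to 75% and obtains 97 per arm, raised to 117 for losses. That paragraph is labelled aim 1, but its content is aim 2.

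The added tests (section 5.g) cover "Chikungunya, Zika, *Coxiella burnetii* (Q-fever), *Bartonella henselae* (Bartonellosis), *Rickettsia typhi* (murine typhus), Japanese B encephalitis, and West Nile virus". Three of these targets are bacterial or rickettsial and four are viral. At this hospital, patients with undifferentiated fever are said to "receive empirical treatment with two or more antimicrobial agents" (section 2, preliminary work).

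Appendix 1, form E, records each agent with its route, total daily dose and total days. It has no start or stop dates and no spectrum class.

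**The concern.** The quantity in the hypothesis is not among the quantities named for analysis or used for sizing. Broad-spectrum is not defined, and it appears neither in section 5.j nor on form E. The word *type* in the analysis list has no categories and no stated comparison, and it is not carried into the paragraph that names the measures.

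The mismatch matters because the intervention can succeed in two ways. A viral diagnosis may lead to antibiotics being stopped, which lowers both total and broad-spectrum use. A rickettsial or bacterial diagnosis may lead to a targeted agent replacing broad-spectrum ones. That lowers broad-spectrum use but may leave total use lower, unchanged or higher.

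At stake is the interpretation of a primary aim. A null result on total use could not be told apart from successful narrowing of treatment, and a fall in total use would not by itself show that broad-spectrum use fell.

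**Working it through.** **1. The plan's own figure.** Inputs from the sample size section: 90% and 75%, 80% power, significance 0.05 (taken as two-sided), equal arms. With unpooled variance:

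n = (1.96 + 0.8416)² × [0.90 × 0.10 + 0.75 × 0.25] / 0.15² = 7.849 × 0.2775 / 0.0225 = 96.8, so 97 per arm.

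This reproduces the stated 97, and 97 × 1.2 = 116.4 gives the stated 117. The figure is valid for the share of patients on any antibiotic. No sample size can be derived for broad-spectrum use, because the documents give no broad-spectrum rate, mean or SD.

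**2. How each measure treats a switch to a targeted agent.**

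- *Any antibiotic use (sizing quantity).* A switched patient still counts as treated, so the switch contributes nothing to the fall from 90% to 75%.
- *Number of antibiotics.* Form E lists every agent given and has no dates, so its count is cumulative. A patient started on two agents and switched to a third counts 3. An untested patient left on the same two counts 2. The count is not raised if the targeted agent was already in the empirical regimen, and the difference narrows or disappears if the result prevents later additions.
- *Total DDD and duration.* The effect depends on what is stopped, when, and how long the targeted course lasts.

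**3. Illustration in agent-days.** All values here are assumed, none comes from the documents, and they are not a treatment proposal. Two empirical broad-spectrum agents are planned for 7 days, the result is acted on at day 3, both agents are stopped, and one targeted agent (not broad-spectrum) is given for L days.

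Broad-spectrum change per bacterial diagnosis = -2 × (7 - 3) = -8. Total change = L - 8.

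| L | Broad-spectrum | Total |
|---|---|---|
| 5 | -8 | -3 |
| 7 | -8 | -1 |
| 8 | -8 | 0 |
| 10 | -8 | +2 |
| 14 | -8 | +6 |

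A viral diagnosis with both agents stopped changes both measures by -8. Let v and b be the proportions of the tested arm with viral and bacterial diagnoses. The mean change per patient is then -8v + b(L - 8) for total use and -8(v + b) for broad-spectrum use.

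| v | b | L | Total | Broad-spectrum |
|---|---|---|---|---|
| 10% | 10% | 7 | -0.9 | -1.6 |
| 10% | 10% | 14 | -0.2 | -1.6 |
| 15% | 5% | 14 | -0.9 | -1.6 |
| 5% | 15% | 14 | +0.5 | -1.6 |

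The broad-spectrum effect is the same in every row. The total is diluted in the first and third rows, nearly null in the second and reversed in the fourth.

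**4. Consequence for the sizing quantity.** The sample size section also assumes that identification of causes rises from 30% to 50%, or 20 points. If antibiotics are stopped only after a new viral diagnosis (assumed), the 15-point fall needs about 15 of those 20 points to be viral. Power for fewer, with p̄ the mean of the two proportions:

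Power = Φ{[|p₁ - p₂| - 1.96 √(2p̄(1 - p̄)/n)] / √([p₁(1 - p₁) + p₂(1 - p₂)]/n)}

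| Viral points | Use in tested arm | Power, n = 97 | Power, n = 117 |
|---|---|---|---|
| 15 | 75% | 79% | 86% |
| 10 | 80% | 50% | 57% |
| 5 | 85% | 18% | 21% |

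Under this assumption the bacterial and rickettsial findings add nothing to the powered contrast, however much broad-spectrum treatment they replace.

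**The case against.** Total antimicrobial consumption is a legitimate outcome. It matches aim 2 and the overall objective in section 4.A, which speaks of antimicrobials in general. This stands, and it is why restating the hypothesis is an acceptable alternative repair.

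Section 5.j lists *type* among the items to be compared, form E names each agent, section 5.i records de-escalation, and aim 3 has an independent physician judge appropriateness. So the data allow a spectrum analysis, and agent classes could be set out in an analysis plan not shown here. This too stands in part. But the protocol itself names the measures and the sizing quantity, and both differ from its hypothesis. Recording agent names makes the repair easy without supplying it. Appropriateness is a separate judgement and does not measure broad-spectrum use.

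Replacing two or more agents by one can lower DDD and duration, and four of the seven targets are viral. Both are correct, so the reversal is a possibility and not a prediction. The cumulative count is the measure most exposed to it.

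A targeted agent might itself be classed as broad-spectrum, in which case the opposing effect would remain. That has to be settled when the list is drawn up.

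**Conclusion.** The concern holds as a mismatch between the hypothesis on one side and the aim 2 measures and sample size on the other. Followed as written, the plan can leave its only hypothesis untested. It is worth correcting, but it does not undermine the data to be collected.

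The size of the distortion cannot be fixed from the documents. Under the assumptions in the illustration, a constant broad-spectrum reduction of 1.6 agent-days per patient appears as a total change between -0.9 and +0.5.

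Three stronger readings are tempting and not supported:

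- *Targeted treatment raises total use, so success would appear as harm.* The documents do not give the targeted agents, course lengths, timing or overlap with empirical treatment, and the total can move either way.
- *The reported 7% and 17% for murine typhus give the number affected, about 8 to 20 of 117* (117 × 0.07 = 8.2; 117 × 0.17 = 19.9). Those rates come from earlier series of febrile patients. They are not shown to apply to patients whose routine work-up was inconclusive, and the step also assumes one added agent per positive result.
- *The trial cannot address its hypothesis at all.* Form E holds agent, daily dose and days, so broad-spectrum use can be derived once it is defined.

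**What to change.** In section 5.j, name broad-spectrum antimicrobial use as the aim 2 outcome that tests the hypothesis. Measure it as DDD or agent-days of drugs on a list written into the protocol. Fix the list before any data are seen, and so before the interim analysis at 25% enrolment. Code from the agent name alone, without reference to arm, since the trial is open-label.

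Keep total DDD, number of agents and duration as supporting measures. State that the cumulative number of agents will not be read as a measure of reduced use. A count of concurrent agents at a fixed time is no substitute on the present form, because form E has no start or stop dates.

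In the sample size section, state that 97 per arm applies to any antibiotic use and not to broad-spectrum use, and correct the aim label.

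If the investigators prefer total use, restate the hypothesis in section 4.A accordingly and leave the measures as they are.

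The cost is a short drug list and a few sentences, with no new data fields. The small downside is that the list must be agreed in advance.
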